8.4. Randomization Criteria

Only those patients meeting all of the following randomization criteria are eligible for randomization:

- 1. Continues to meet all inclusion and exclusion criteria, including urine and blood test results and is successfully and consistently utilizing the diary system.
- 2. Patient's FM pain satisfies the following criteria, as assessed by diary pain scores (24 hour recall):
 - a. A mean pain intensity score ≥4 and ≤9 on the 11-point (0-10) NRS scale for the 7 days immediately preceding Visit 2, and

- b. No more than 2 individual days with a score <4 on the 7 days immediately preceding Visit 2, and
- c. No score of 10 on any of the 7 days immediately preceding Visit 2, and
- d. Pain scores recorded on at least 5 out of the 7 days immediately preceding Visit 2.

If the patient does not satisfy these randomization criteria, the patient has failed to qualify for this study and should be considered a screen failure, with the reason documented. With Sponsor approval, if the patient is otherwise considered a qualified and compliant patient, Visit 2 may be delayed due to acceptable extenuating circumstances. There is no requirement for a Follow-Up visit for screen failures.

8.5. Patient Withdrawal Criteria

In accordance with the Declaration of Helsinki, human subjects have the right to withdraw from the study at any time for any reason. The Investigator and Tonix also have the right to remove patients from the study. Additional information regarding withdrawal or discontinuation of patients is described in detail in Section 11.5.2.

9. TREATMENT OF PATIENTS

9.1. Prior and Concomitant Medications

Patients who are taking certain medications to manage their FM are eligible for the study if they are willing and able (and it is medically reasonable for them) to be withdrawn from those medications that are specifically excluded by the protocol and they agree to refrain from further usage during this study. The specific medications that must be withdrawn include milnacipran, pregabalin, duloxetine, tramadol, gabapentin, any form of cyclobenzaprine (AMRIX®, FEXMID® or generic cyclobenzaprine), tapentadol, amitriptyline and other tricyclic antidepressants, trazodone, narcotics/opioids and naltrexone (including CONTRAVE®). In addition, certain other medications are prohibited and may require washout, or exclusion of patients for whom washout is not appropriate (e.g., benzodiazepines, anticonvulsants (except when used as migraine prophylaxis), levomilnacipran, mirtazapine, nefazodone, St. John's wort, phentermine, diethylproprion, muscle relaxants (e.g., methocarbamol, baclofen, carisoprodol), and systemic use of strong CYP3A4 inhibitors as defined in Appendix 1 (i.e., topical use is not excluded).

All patients undergoing washout must complete a 3-week drug-free interval prior to the Baseline/Randomization visit (Visit 2); this will provide two weeks of washout prior to the 7 days leading up to Visit 2 when baseline efficacy data will be collected on the daily diary. Any patient with a positive screening UDS who is washing off an opioid, amphetamine, or benzodiazepine must return to the clinic for a repeat UDS before they begin their 7-day baseline data collection period leading up to Visit 2.

In general, patients utilizing benzodiazepines on a chronic or regular basis should not be considered for the study; however, washout may be considered for those patients utilizing them only on an occasional or as-needed basis (e.g, three times per week or less, on average). Buspirone for anxiety is allowed during the trial.

Several benzodiazepines are not easily detected by the in-clinic urine dipstick; therefore, patients positive for benzodiazepines at Screening and deemed appropriate for washout will require a centrally-interpreted repeat UDS conducted prior to the beginning of the 7-day baseline data collection period prior to V2. All other repeat urine drug screens can be conducted on-site. All repeat UDS results must be confirmed negative before the patient can be randomized.

Patients using non-benzodiazepine hypnotics (e.g., zolpidem, eszopiclone, zaleplon) on a chronic, nightly basis should not be enrolled; however, patients utilizing these medications on an infrequent or occasional basis only (e.g., three times per week or less, on average) may be considered. Similar to the benzodiazepines, drugs in this class of medication can negatively impact sleep architecture; therefore, patients utilizing either non-benzodiazepines or benzodiazepines should be discussed with the Medical Monitor early during the screening process to determine their suitability for the study and to determine whether washout is clinically advisable. Patients washing off non-benzodiazepines should not be randomized if they are unable to discontinue their use and remain drug-free through their 7-day baseline data collection period leading up to Visit 2. The patient's ability to successfully discontinue their use of excluded sleep therapies should be carefully assessed, since UDS testing is not available for non-benzodiazepine hypnotics.

After randomization, sedating antihistamines (e.g., diphenhydramine, hydroxyzine) may be used as needed for insomnia; however, patients will need to refrain from their use during the week of baseline data collection leading up to Visit 2. Patients should track their use of sedating antihistamines in between study visits so that changes in usage during the course of the study can be tracked and recorded.

The use of melatonin, ramelteon, and valerian root is not restricted. Similarly, the use of cannabidiol (CBD) products is not restricted, but like all other allowed concomitant medications, its usage should have been stable for at least 30 days prior to randomization, and usage should remain stable during the study. Additionally, the use of CBD products should not be started after randomization. All CBD products should be added to the concomitant medication source and case report form (CRF).

Due to the exclusion of all opioids during the Treatment Phase of the study, patients requiring opioids on a regular or frequent basis for any indication should not be considered. In addition, patients with neuropathic pain in addition to fibromyalgia should not be washed off of gabapentin, pregabalin or any other anticonvulsant, and therefore should not be considered for the study.

At Screening Visit 1 and after signing the written informed consent, any required washout should be discussed with the patient and plans made for an appropriate schedule for reducing/stopping any excluded medications. This down titration and withdrawal must be accomplished so that the patient is medication free for at least 21 days prior to randomization. This will provide 14 days off the excluded medication before the patient starts the 7-day run-in phase during which critical baseline efficacy data are collected by means of the daily diary. Any additional time required for down-titration would be in addition to this 21-day washout requirement. For this reason, patients can remain in screening for up to 35 days, which provides an additional 2 weeks for down-titration, if required. For extenuating circumstances, the duration of the Screening period may be increased to up to 49 days with Medical Monitor approval.

Other chronic prescription or over-the-counter medication not specifically excluded by an exclusion criterion may be continued in the study, provided that the patient has been on this medication for at least 30 days at a stable dose (except for allowed antidepressants, which require 90 days at stable dose) from the date of randomization, and usage is expected to remain stable throughout the study. Allowed medications include, but are not limited to, hormonal therapy (contraceptives and replacement therapy), anti-hypertensive agents, lipid-lowering medications, selective serotonin reuptake inhibitors (SSRI) and other allowed antidepressants (e.g., venlafaxine, desvenlafaxine, bupropion, vilazodone).

Acetaminophen (up to 3000 mg/day) and non-steroidal anti-inflammatory drugs (NSAIDs) may be continued in a stable fashion for osteoarthritis or other allowed indications (e.g., aspirin for cardioprophylaxis), or used as needed for other sources of acute, minor pain. Note that acetaminophen and NSAIDs may be taken either on a regular basis, or on an as-needed (prn) basis; however, if used as-needed, the Investigator should ascertain the patient's typical pattern of usage (e.g., average dosage and frequency per defined time interval) so that this information can be recorded on the CRF. Any significant change in the patient's usage of any medication, including those taken only as needed, should result in an update to the CRF. The CRF entry for any prn medication is expected to include an estimation of the patient's average dosage and frequency per defined time interval.

Patients on allowed antidepressants due to a history of depression should only be considered for the study if no changes in antidepressant agent or dose have occurred during the 90 days leading up to randomization, and no changes are anticipated or planned during the treatment phase of the study. In addition, FM patients with comorbid depression who are being treated with duloxetine, milnacipran, levomilnacipran, monoamine oxidase inhibitors, or tricyclic antidepressants should in general not be considered for the study since washout of these agents could destabilize their psychiatric status.

NOTE: Participating patients receiving treatment with antidepressants should be cautioned about the possibility of serotonin syndrome, which has been reported in patients receiving cyclobenzaprine with SSRIs, serotonin-norepinephrine reuptake inhibitors (SNRI) and related agents. This will be included in the ICF.

New medications that are deemed required, in the opinion of the Principal Investigator or another physician, will be allowed, including medications needed to treat adverse events. After randomization, if there is a requirement for treatment with an acute opioid or other treatment that may confound the evaluation of pain at critical times during the study (defined as the week prior to Visits 3, 4, 5 or 6), the Investigator may consult with the Medical Monitor to potentially delay the study visit until the medication is no longer needed. At a minimum, no opioid/narcotic should have been utilized within 2 days of a study visit, and ideally there will have been no usage during the 7 days prior to these visits. While it is understood that opioid usage will occasionally be necessary and unavoidable, it could have consequences on the patient's data.

Similarly, if there is a requirement for acute, short-term opioid usage during the screening phase, the start of the 7-day run-in phase should be delayed to ensure at least 2 days between the last opioid dose and the beginning of the 7-day run-in phase. In other words, there may be some circumstances when the unexpected requirement for short-term opioid usage, specifically due to an *acute* medical, dental or surgical condition, does not require the full 21-day washout. This provision only applies to *acute* pain conditions – not to opioid usage due to a flare in patient's FM or other chronic pain condition. Any requirement for acute opioid usage during the screening phase should be brought to the attention of the Medical Monitor to ensure adequate washout prior to randomization.

Patients should refrain from drinking grapefruit juice or eating grapefruit during the study due to its ability to inhibit CYP3A4 activity. Aside from this restriction, there are no other food or fluid restrictions in this study except for the instructions pertaining to dosing (Section 10.2).

Patients using teeth-whitening products such as whitening strips or prescription whitening products must agree to discontinue their use from the day of randomization until the end of their study participation.

Any concomitant medications or other treatments must be recorded in the patient's medical record and case report form along with the dose and dates of treatment.

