16.3. Written Informed Consent

It is the responsibility of the Investigator to obtain signed written informed consent from each potential study patient prior to the conduct of any screening or other study procedures. This written informed consent will be obtained after the methods, objectives, and potential risks of the study have been fully explained to the potential patient. The Investigator must explain to each patient that he or she is completely free to refuse to enter the study or to withdraw from it at any time. NOTE: Patients on antidepressant therapy should be warned of a potential serious drug interaction and should be advised to contact their study site immediately if they experience any symptoms that might represent possible serotonin syndrome, including fever, confusion or agitation, hallucinations, sweating, high or low blood pressure, rapid heart rate, tremor, muscle rigidity or nausea, vomiting or diarrhea.

The patient should also be asked in the ICF for permission for the Principal Investigator or his designee to contact the patient's other personal physicians, as appropriate, concerning participation in the study.

The method of obtaining and documenting informed consent and the contents of the ICF will comply with ICH GCP guidelines, the requirements of 21 CFR Part 50, "Protection of Human Subjects," the Health Insurance Portability and Accountability Act (HIPAA) regulations, and all other applicable regulatory requirements. A properly executed written ICF shall be read, signed, and dated by each patient prior to entering the trial or prior to performing any study procedure. The original signed and dated ICF will be kept on file at the study site. Patients will be given a copy of the signed ICF and will be informed of any new developments during the course of the study that might influence their continued participation in the study.

The Investigator or a qualified designee will be available to answer each patient's questions throughout the study, and all questions must be answered to the patient's satisfaction. If the protocol is amended and a revised ICF is introduced during the study, each patient's further consent must be obtained. The new version of the ICF must be approved by the EC/IRB, prior to subsequently obtaining each patient's consent.

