20. APPENDICES

APPENDIX 1 List of CYP3A4 Inhibitors

Taken from Table 3-2, Examples of clinical inhibitors for P450-mediated metabolisms (for concomitant use clinical Drug-Drug Interaction studies and/or drug labeling) (03/06/2020). Excluded strong CYP3A4 inhibitors are listed in the far-left column of the table.

	Strong Inhibitors	Moderate Inhibitors	Weak Inhibitors
	≥ 5-Fold Increase in AUC or	≥ 2 but < 5-Fold Increase in	≥ 1.25 but < 2-Fold Increase in
	> 80% Decrease in CL	AUC or 50-80% Decrease in CL	AUC or 20-50% Decrease in CL
CYP3A4	boceprevir,	aprepitant,	chlorzoxazone,
	cobicistat(h),	ciprofloxacin,	cilostazol,
	danoprevir and ritonavir(j),	conivaptan(l),	cimetidine,
	elvitegravir and ritonavir(j),	crizotinib,	clotrimazole,
	grapefruit juice(k), indinavir	cyclosporine,	fosaprepitant,
	and ritonavir(j),	diltiazem(m),	istradefylline,
	itraconazole(h),	dronedarone(h),	ivacaftor(h),
	ketoconazole,	erythromycin,	lomitapide,
	lopinavir and ritonavir(h,j),	fluconazole(f),	ranitidine,
	paritaprevir and ritonavir and	fluvoxamine(a),	ranolazine(h),
	(ombitasvir and/or	imatinib,	ticagrelor(h)
	dasabuvir)(j),	tofisopam,	
	posaconazole,	verapamil(h)	
	ritonavir(h,j),		
	saquinavir and ritonavir(h,j),		
	telaprevir(h),		
	tipranavir and ritonavir(h,j),		
	telithromycin,		
	troleandomycin,		
	voriconazole		
	clarithromycin(h),		
	idelalisib,		
	nefazodone,		
	nelfinavir(h)		
	nemnavir(n)	2.1.4	

Abbreviation: CYP3A4 = cytochrome P450 subtype 3A4

- (a) Strong inhibitor of CYP1A2 and CYP2C19. Moderate inhibitor of CYP3A and Weak inhibitor of CYP2D6.
- (f) Strong inhibitor of CYP2C19 and moderate inhibitor of CYP2C9 and CYP3A.
- (h) Inhibitor of P-gp (defined as those increasing AUC of digoxin to ≥1.25-fold).
- (j) Ritonavir is usually given in combination with other anti-HIV or anti-HCV drugs in clinical practice. Caution should be used when extrapolating the observed effect of ritonavir alone to the effect of combination regimens on CYP3A activities.
- (k) The effect of grapefruit juice varies widely among brands and is concentration-, dose-, and preparation-dependent. Studies have shown that it can be classified as a "strong CYP3A inhibitor" when a certain preparation was used (e.g., high dose, double strength) or as a "moderate CYP3A inhibitor" when another preparation was used (e.g., low dose, single strength).
- (1) The classification is based on studies conducted with intravenously administered conivaptan.

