Nervous System and Psychiatric. Seizures; ataxia; vertigo; dysarthria; tremors; hypertonia; convulsions; muscle twitching; disorientation; insomnia; depressed mood; nypertonia; convuisions; muscle twitching; disorientation; insormia; depressed mood; abnormal sensations; anxiety; agitation; psychosis; abnormal thinking and dreaming; hallucinations; excitement; paresthesia; diplopia; serotonin syndrome; neuroleptic malignant syndrome; decreased or increased libido; abnormal gait; delusions; aggressive behavior; paranoia; peripheral neuropathy; Bell's palsy; afteration in EEG patterns; extrapyramidal symptoms.

Respiratory: Dyspnea.

Skin: Sweating; photosensitization; alopecia.

Special Senses: Ageusia; tinnitus.

Urogenital: Urinary frequency and/or retention; impaired urination; dilatation of urinary tract; impotence; testicular swelling; gynecomastia; breast enlargement; galactorrhea.

DRUG INTERACTIONS

Based on its structural similarity to tricyclic antidepressants, AMRIX may have life-threatening interactions with MAO inhibitors [see Contraindications (4)], may enhance the effects of alcohol, barbiturates, and other CNS depressants, may enhance the seizure risk in patients taking tramadol, or may block the antihypertensive action of guanethidine and similarly acting compounds.

Postmarketing cases of serotonin syndrome have been reported during combined use

of cyclobenzaprine and other drugs, such as SSRIs, SNRIs, TCAs, tramadol, bupropion, meperidine, verapamil, or MAO inhibitors [see Warnings and Precautions (5.1)].

USE IN SPECIFIC POPULATIONS

Pregnancy

Risk Summary

Available data from case reports with AMRIX use in pregnancy have not identified a drug-In rats, decreased pup body weight and survival was noted at cyclobenzaprine doses \geq 10 mg/kg/day (approximately \geq 3 times the maximum recommended human dose (MRHD) of 30 mg/day), when administered orally during pregnancy and lactation

The estimated background risk of major birth defects and miscarriage for the indicated populations is unknown. All pregnancies have a background risk of birth defect, loss, or other adverse outcomes. In the US general population, the estimated background risk of major birth defects and miscarriage in clinically recognized pregnancies is 2% to 4% and 15% to 20%, respectively.

Animal Data

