16.2 Storage and Handling

Dispense in a tight, light-resistant container as defined in the USP/NF.

Stora at 25°C (77°F); excursions permitted to 15 - 30°C (59 - 86°F) [see USP

Controlled Room Temperature].

AMRIX® (cyclobenzaprine hydrochloride extended-release capsules)

PATIENT COUNSELING INFORMATION

- See FDA-approved patient labeling (Patient Information).

 Instruct patients to swallow AMRIX capsules intact or to sprinkle capsule contents
- on a tablespoon of applesauce and swallow immediately without chewing.

 Advise patients to stop taking AMRIX and to notify their physician right away if they experience symptoms of an allergic reaction, such as difficulty breathing,
- Nives, swelling of face or tongue, or itching.
 Advise patients that AMRIX should not be taken with MAO inhibitors or within 14 days after their discontinuation.
- Caution patients about the risk of serotonin syndrome with concomitant use of AMRIX and other drugs, such as SSRIs, SNRIs, TCAs, tramadol, bupropion, meperidine, verapamil, or MAO inhibitors. Advise patients of the signs and symptoms of serotonin syndrome [see Warnings and Precautions (5.1)] and instruct patients to seek medical care immediately if they experience these
- Advise patients to stop taking AMRIX and to notify their physician right away if they experience arrhythmias or tachycardia.

 Advise patients that AMRIX may enhance the impairment effects of alcohol. These effects may also be seen if AMRIX is taken with other CNS depressants.
- Caution patients about operating an automobile or other hazardous machinery until it is reasonably certain that AMRIX therapy will not adversely affect their
- ability to engage in such activities.

 Advise patients to take AMRIX at approximately the same time each day.

Distributed By: Teva Pharmaceuticals USA, Inc. Parsippany, NJ 07054

Manufactured By:

Adare Pharmaceuticals, Inc.

Vandalia, OH 45377

AMR-011

Rev. 5/2020

US Patent Nos. 7387793, 7544372, 7790199, 7820203, 7829121, 8877245, 9375410,

© 2020 Teva Pharmaceuticals USA, Inc.

All rights reserved.

PATIENT INFORMATION

AMRIX® (am-rix)

(cyclobenzaprine hydrochloride extended-release capsules)

What is AMRIX?

AMRIX is a prescription medicine used along with rest and physical therapy to help treat muscle spasm due to acute, painful musculoskeletal problems.

AMRIX should only be used for up to 2 or 3 weeks. It is not known if AMRIX is effective when used for longer periods.

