4.4.1 Opioid Usage

In order to minimize confounding issues related to concomitant usage of opioids, investigators have been asked to identify candidates for this clinical trial that are not currently using chronic opioids. However, it is understood by the Sponsor that opioid usage is sometimes unavoidable for acute conditions. In the event that an opioid is required for the management of an acute pain condition, the patient will be instructed to contact the site immediately so that appropriate management decisions can be implemented and accurate medication records obtained. In addition, when feasible, study visits may be delayed to avoid the contamination of data by recent

Protocol: TNX-CY-F307 Page 16 of 45

Final v1.0

opioid usage. At a minimum, no opioid/narcotic should be utilized within 2 days of a study visit, and ideally there will be no usage during the 7 days prior to any visit.

A listing of concomitant medication CRF data identifying the use of opioids will be reviewed by the project team and approved by the Sponsor prior to database lock and unblinding, and will be used to flag records in the analysis database and in the by-patient concomitant medication listings. These flagged records will also be utilized to identify records to be censored in the sensitivity analysis described in Section 10.1.3.

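### The protocol requires the serotonin-syndrome caution only for antidepressant users, although its own attached label also names verapamil, which patients may take throughout treatment

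*Protocol*

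**What the plan says.** Two places in the protocol body deal with serotonin syndrome.

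- Section 9.1 has a note that "Participating patients receiving treatment with antidepressants should be cautioned about the possibility of serotonin syndrome". It ties the reports to SSRIs, SNRIs and related agents, and says the caution will appear in the consent form.
- Section 16.3 says: "Patients on antidepressant therapy should be warned of a potential serious drug interaction and should be advised to contact their study site immediately" if symptoms appear, and then lists the symptoms.

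Appendix 2 is the label of the reference cyclobenzaprine product. Its drug-interactions section (label Section 7) refers to postmarketing cases during combined use "of cyclobenzaprine and other drugs, such as SSRIs, SNRIs, TCAs, tramadol, bupropion, meperidine, verapamil, or MAO inhibitors". Its patient-counselling section (label Section 17) asks prescribers to caution patients about concomitant drugs "such as SSRIs, SNRIs, TCAs, tramadol, bupropion, meperidine, verapamil, or MAO inhibitors. Advise patients of the signs and symptoms of serotonin syndrome". Label Section 5.1 and the patient leaflet also name verapamil.

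On what patients may take, Section 9.1 says: "Allowed medications include, but are not limited to, hormonal therapy (contraceptives and replacement therapy), anti-hypertensive agents, lipid-lowering medications". It adds a later allowance: "New medications that are deemed required, in the opinion of the Principal Investigator or another physician, will be allowed". Exclusion criterion 13 removes strong CYP3A4 inhibitors, and Appendix 1 explains: "Excluded strong CYP3A4 inhibitors are listed in the far-left column of the table". Verapamil is in the moderate column of that table.

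**The concern.** The protocol carries a warning from the attached label into this trial, but for only part of the label's list. It leaves out a drug on that list which it allows patients to take. Label Section 5.1 describes the syndrome as potentially life-threatening and advises close watching, above all when treatment starts or the dose rises. This trial does both: dosing starts on Day 1 and doubles on Day 15.

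A site following the two notes exactly would give an SSRI user the symptom list and the instruction to call at once. It would not be required to give either to a verapamil user. What is at stake is how early a rare but serious event is recognised. The estimand, the efficacy analysis and the validity of the comparison are not affected.

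**Working it through.** The check sets the label's list against the protocol's medication rules and the two notes. The plan states no figure to reproduce.

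**Step 1. Classify each entry on the label list** (Appendix 2, label Sections 7 and 17).

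| Label entry | Status in the trial | Reached by the notes in 9.1 and 16.3? |
|---|---|---|
| SSRIs | Allowed if stable (9.1) | Yes |
| SNRIs | Venlafaxine and desvenlafaxine allowed (9.1); duloxetine, milnacipran and levomilnacipran excluded | Yes |
| Bupropion | Allowed if stable (9.1) | Yes |
| Verapamil | Not excluded | **No** |
| TCAs | Must be withdrawn (inclusion 6) | Yes, but moot |
| MAO inhibitors | Must be washed out (exclusion 13) | Yes, but moot |
| Tramadol | Excluded; acute use only | No |
| Meperidine | Excluded as an opioid; acute use only | No |

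**Step 2. Count.**

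- Label entries: 8. Antidepressants: 5. Not reached by the notes: 8 − 5 = 3.
- Entries that may be taken as stable long-term treatment: SSRIs, some SNRIs, bupropion and verapamil = 4. Reached by the notes: 3. Missed: 4 − 3 = 1, which is verapamil.

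**Step 3. Confirm that verapamil is allowed.** The protocol never permits it by name, so the conclusion comes from three rules read together:

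- The Appendix 2 leaflet describes verapamil as a blood-pressure medicine, and Section 9.1 lets anti-hypertensives continue after at least 30 days at a stable dose.
- Exclusion 13 reaches strong CYP3A4 inhibitors only, and Appendix 1 places verapamil among the moderate ones.
- Section 9.1 allows new medication that a physician considers required, with no exception for verapamil.

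**Step 4. Planned length of co-exposure.** Dosing runs from Day 1 to Day 98, which is 98 nights. The first 14 are at 2.8 mg, so nights at 5.6 mg = 98 − 14 = 84. This applies to a patient who takes verapamil throughout and follows the dosing schedule.

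**Step 5. See whether another provision gives the same warning.**

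- The Visit 2 instructions (11.2.4) tell patients to call about oral lesions. They do not mention serotonin syndrome.
- The Week 2 reminder to report tolerability problems (11.3) goes to everyone, but comes after the first two weeks of dosing and lists no symptoms.
- Adverse-event questions (12.3.1) are asked at every visit and are deliberately non-leading. After Week 2 the treatment visits are four weeks apart.
- For acute opioids, SAP Section 4.4.1 says "the patient will be instructed to contact the site immediately so that appropriate management decisions can be implemented". This gives some cover for tramadol and meperidine, though its purpose is managing opioid use. It does not concern verapamil.

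None of these requires that a verapamil user receive the symptom list and the advice to call.

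**The case against.** The strongest objection is the consent form. Section 9.1 says the caution will be in it, and Section 16.3 requires every patient to read it, sign it and keep a copy after the risks have been explained. The only separate consent described is for pharmacogenomics. A verapamil user will therefore hold a document that contains some serotonin-syndrome text. If that text addresses everyone, no patient is under-warned and the defect is editorial. This stands as a limit, because the form was not available for review. It does not change what the protocol requires: both notes direct the caution to antidepressant users.

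Second, Appendix 2 is part of the protocol, and Section 16.1 requires investigators to know the risks it describes. The person giving the caution therefore has the verapamil instruction to hand. That is true and reduces the risk. However, the operative text on whom to caution points that investigator to antidepressants only.

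Third, the label covers 15 to 30 mg of an oral extended-release product, and the study dose is 5.6 mg sublingually, about 2.7 to 5.4 times lower (15 / 5.6 = 2.7; 30 / 5.6 = 5.4). The risk may well be smaller. Yet the protocol already treats the warning as relevant at this dose for antidepressants, and gives no reason for leaving verapamil out.

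Fourth, few patients are likely to be concerned. The cardiac exclusions (criterion 9) and the age limit of 65 will remove some verapamil users. This stands, and it is why the point is modest.

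**Conclusion.** The concern holds. The protocol's rule on whom to caution is narrower than the safety source attached to it, and the gap includes a drug that patients may take throughout treatment. Verapamil is the main omission: one of the four listed entries open to long-term use. Acute tramadol or meperidine use is a smaller gap of the same kind.

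The change is worth making because the event can be serious and the correction is cheap; the number of patients at risk is not known to be large. The documents give neither a rate of verapamil use nor a rate of serotonin syndrome, so no patient count is offered. The conclusion rests on reading the allowance for anti-hypertensives as including verapamil, and on the protocol text alone. A broader consent form would reduce the matter to aligning two notes.

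**What to change.** Reword the notes in Sections 9.1 and 16.3, and the matching consent text, so that the caution, the symptom list and the advice to contact the site go to all participants. This also covers acute tramadol or meperidine use and verapamil started after randomization.

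The minimum alternative is to direct them to anyone who takes, or is newly prescribed, any drug on the Appendix 2 list, naming verapamil explicitly, and tramadol or meperidine where used acutely. If the consent form already warns everyone, only the two notes need to be aligned.

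The cost is two protocol sentences and possibly one consent sentence, with no new procedure or visit. The change needs IRB approval (Section 15.1) and, if the consent form is revised while the trial is running, renewed consent from each patient (Section 16.3). Addressing everyone also means that some patients not at risk will read the warning.
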